5.3. Dose Modification and Discontinuation

Modification of study treatment (interruption, reduction, and/or permanent discontinuation) may be indicated if an AE is judged (by the Investigator) to be possibly related to CTL-002 and/or nivolumab/cemiplimab. In any such cases it is also recommended to consult the Sponsor's Medical Monitor.

5.3.1. Dose Reduction

Nivolumab/Cemiplimab intra-subject dose escalation or reductions are not allowed. Dosing may only be interrupted, delayed, or discontinued. The same applies for CTL-002.

5.3.2. Permanent Dosing Interruption (Discontinuation)

Permanent discontinuation of both CTL-002 and nivolumab/cemiplimab is required/recommended under the following criteria and following [Table 4](#) recommendations:

- Subjects who experience any at least possibly CTL-002-, or nivolumab/cemiplimab related **Grade 4 AE**
- Subjects who experience any at least possibly CTL-002-, or nivolumab/cemiplimab-related **Grade ≥ 2 immune-related myocarditis**
- Subjects who experience any at least possibly CTL-002- or nivolumab/cemiplimab-related **Grade ≥ 3 immune-related pneumonitis, adrenal insufficiency**
- Subjects who experience any at least possibly CTL-002-, or nivolumab/cemiplimab-related immune-related **hepatitis**
 - Subjects with no tumor involvement in the liver with \geq Grade 3 AST or ALT or total bilirubin elevation
 - Subjects with tumor involvement of the liver with AST or ALT increases to $> 10 \times$ ULN or total bilirubin increases to $> 3 \times$ ULN

- Subjects who experience **Stevens-Johnson syndrome (SJS)**.
- Subjects who experience any other at least possibly CTL-002- or nivolumab/cemiplimab-related **Grade 3 AE** that persists despite optimal supportive treatment measures
- Subjects who experience any other at least possibly CTL-002- or nivolumab/cemiplimab-related AE of any Grade that **in the opinion of the Investigator requires permanent discontinuation** (SRC ad-hoc confirmation for discontinuation recommended for this case)
- Subjects who experience **recurrent Grade 3 toxicities**

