5.2.7. Management of Immune-related Adverse Events

The supportive care guidelines described in this section can be modified by the treating physician/Investigator as deemed medically necessary or as appropriate without requiring a protocol amendment or being considered a protocol deviation.

An irAE is defined as an off-target side effect associated with exposure of immunogenic drug and is consistent with immune mechanism. In the process of identification of irAE any possible etiology of neoplastic, infectious, metabolic, toxin, or any other factor should be ruled out, serologic, histologic (biopsy), and/or immunologic results should be obtained to evaluate the differential diagnosis and/or support an immune-mediated cause.

An irAE should be documented as “Adverse Event of Special Interest”, and it is recommended to involve the medical monitor at first incidence and subsequently as needed for follow-up. Details of the diagnostic work-up will be requested by the study team.

In order to help health care providers who are not involved with the subject’s cancer treatment, to identify that subjects have received immune-oncology therapy as well as to recognize rare or subtle

symptoms of immune-oncology toxicity, subjects will be provided with immune-oncology wallet cards.

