		Resume if colitis or diarrhea improves and remains at Grade 0 to 1 after corticosteroid taper to ≤ 10 mg/day prednisone or equivalent. Permanently discontinue if no complete or partial resolution within 12 weeks of initiating steroids or inability to reduce prednisone to ≤ 10 mg/day (or equivalent) within 12 weeks of initiating steroids.	
	Grade 3 or 4 diarrhea or colitis	Permanently discontinue	Initial dose of 1 to 2 mg/kg/day prednisone or equivalent followed by a taper
Hepatitis with no tumor involvement in liver	Grade 2 with AST or ALT $> 3\times$ and $\leq 5\times$ ULN, or total bilirubin to $> 1.5\times$ and $\leq 3\times$ ULN, regardless of baseline value	Withhold	Initial dose of 1 to 2 mg/kg/day prednisone or equivalent followed by a taper
		Resume if hepatitis improves and remains at Grade 0 to 1 after corticosteroid taper to ≤ 10 mg/day prednisone or equivalent or returns to baseline AST or ALT after completion of corticosteroid taper. Permanently discontinue if no complete or partial resolution within 12 weeks of initiating steroids or inability to reduce prednisone to ≤ 10 mg/day (or equivalent) within 12 weeks of initiating steroids.	
	Grade 3 or 4 with AST or ALT $> 5\times$ ULN, or total bilirubin $> 3\times$ ULN, regardless of baseline value	Permanently discontinue	Initial dose of 1 to 2 mg/kg/day prednisone or equivalent followed by a taper
Hepatitis with tumor involvement in the liver^b	1.) Baseline AST/ALT is $> 1\times$ and $\leq 3\times$ ULN and increases to $> 5\times$ and $\leq 10\times$ the ULN or	Withhold	Initial dose of 1 to 2 mg/kg/day prednisone or equivalent followed by a taper
	2.) Baseline AST/ALT is $> 3\times$ and $\leq 5\times$ ULN and increases to $> 8\times$ and $\leq 10\times$ the ULN	Resume in subjects with complete or partial resolution (Grade 0 to 1) after corticosteroid taper to ≤ 10 mg/day prednisone or equivalent or returns to baseline AST or ALT after completion of corticosteroid taper. Permanently discontinue if no complete or partial resolution within 12 weeks of initiating steroids or inability to reduce prednisone to ≤ 10 mg/day (or equivalent) within 12 weeks of initiating steroids.	
	AST or ALT increases to $> 10\times$ ULN or total bilirubin increases to $> 3\times$ ULN	Permanently discontinue	Initial dose of 1 to 2 mg/kg/day prednisone or equivalent followed by a taper

Table 4 Recommended Treatment Modifications for Checkpoint Blockade in combination with CTL-002

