Other immune-related adverse reactions (including but not limited to myositis, solid organ transplant rejection, graft-vs-host disease, myasthenia gravis, pericarditis, immune thrombocytopenic purpura, vasculitis, arthralgia, arthritis, muscular weakness, myalgia, polymyalgia rheumatica, Sjogren's syndrome, keratitis, stomatitis)	Grade 2 or 3 based on type of reaction (first occurrence)	Withhold dose(s)	Initiate symptomatic management including initial dose of 1 to 2 mg/kg/day prednisone or equivalent followed by a taper
		Resume if other immune-related adverse reaction improves and remains at Grade 0 to 1 after corticosteroid taper to ≤10 mg/day prednisone or equivalent.	
	– Grade 3 based on type of reaction or Grade 4 – Grade 3 or 4 pericarditis – Recurrent Grade 3 immune-related adverse reaction – Persistent Grade 2 or 3 lasting 12 weeks or longer despite treatment modification – Inability to reduce corticosteroid dose to 10 mg or less prednisone or equivalent per day within 12 weeks of initiating steroids	Permanently discontinue treatment	Initial dose of 1 to 2 mg/kg/day prednisone or equivalent as clinically indicated followed by a taper
Infusion-related reactions (refer to Section 5.2.5)	Grade 1 or 2	Interrupt or slow the rate of infusion	Initiate symptomatic management
	Grade 3 or 4	Permanently discontinue treatment	

Abbreviations: ALT = alanine aminotransferase; AST = aspartate aminotransferase; DRESS = Drug Rash with Eosinophilia and Systemic Symptoms; ULN = upper limit of normal; SJS = Stephen-Johnson syndrome; SmPC = Summary of Product Characteristics; TEN = toxic epidermal necrolysis.

Note: Toxicity should be graded with the current National Cancer Institute Common Terminology Criteria for Adverse Events (NCI-CTCAE).

^a Recommendation for the use of hormone replacement therapy is provided below.

^b If AST and ALT are less than or equal to ULN at baseline, withhold or permanently discontinue based on recommendations for hepatitis with no liver involvement.

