5.3.4. Recommencement of Dosing

In general, subjects may be considered for recommencement of treatment once

- A toxicity resolves to **Grade ≤ 1** (provided that the toxicity was not recurrent) or
- When a toxicity **is stable and manageable through supportive/medical therapy and in the Investigator’s opinion** and in agreement with the Sponsor Medical Monitor **it appears safe to recommence treatment**

For Part A (Phase 1), CTL-002 recommencement of treatment may be at the initial dose level or one dose level reduced, based upon the discretion of the Investigator ideally in agreement with the Sponsor Medical Monitor. For Part B (Phase 2a) of the study, recommencement of treatment should be at the same dose based upon the discretion of the Investigator ideally in agreement with the Sponsor Medical Monitor. There are no intra-subject dose escalation or reductions allowed. Dosing may only be interrupted, delayed, or discontinued.

For nivolumab, the dose is fixed at 240 mg and no dose adjustment is permitted under any circumstance apart from those provided in the label.

For cemiplimab, the dose is fixed at 350 mg and no dose adjustment is permitted under any circumstance apart from those provided in the label.

Treatment modifications for irAE and infusion-related reactions (Grade 1 to 4) should be handled according to the guidelines in [Section 5.2.5](#).

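### The liver-tumor stopping line in Section 5.3.2 omits the baseline condition of Table 4 footnote b, and Section 5.3.4 permits restart without Table 4's conditions and points immune-related events to the wrong section

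*Protocol*

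**What the plan says.** **Stopping.** Section 5.3.2 says that permanent discontinuation of both drugs "is required/recommended under the following criteria and following" the Table 4 recommendations. Its hepatitis entry has two lines. Without liver tumor, the stop is Grade 3 or higher AST, ALT or bilirubin. With liver tumor ("Subjects with tumor involvement of the liver with AST or ALT increases to"), it is above 10 x ULN, or bilirubin above 3 x ULN. Neither line mentions baseline values. A later residual line covers any other related Grade 3 event "that persists despite optimal supportive treatment measures".

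Table 4 (Section 5.2.7.1) has separate hepatitis rows with and without liver tumor. Footnote b, attached to the liver-tumor row, concerns subjects whose AST and ALT do not exceed the ULN at baseline: "withhold or permanently discontinue based on recommendations for hepatitis with no liver involvement".

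**Restarting.** Table 4 gives resume conditions event by event. Section 5.3.4 gives a general rule with two alternatives: the toxicity is Grade 1 or below and not recurrent, or it "is stable and manageable through supportive/medical therapy" and the investigator, in agreement with the Medical Monitor, considers restart safe. Its last sentence refers immune-related and infusion-related events to Section 5.2.5.

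**Status of the guidance.** Section 5.2.7 lets the investigator adapt its supportive care guidelines "without requiring a protocol amendment or being considered a protocol deviation".

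**The concern.** A site managing a rise in liver enzymes will probably go to the section headed permanent discontinuation. For a subject with liver tumor and normal baseline transaminases, that section's explicit line and the footnote to Table 4 give different AST/ALT levels for the same decision. A site deciding whether to restart after a Grade 2 immune-related event finds a looser rule in Section 5.3.4 than in Table 4, and a cross-reference that leads away from Table 4.

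Patient safety comes first: hepatitis is among the risks of the combination described in Section 1.8. The decisions also enter the reported data. Adverse events leading to discontinuation are summarized (Section 8.3.2). Stopping for toxicity makes a subject evaluable without completing the core cycles (Section 3.5). Ending treatment for a treatment-related event is mentioned in the definition of the Efficacy Evaluable Analysis Set (Section 8.2).

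**Working it through.** No sample size or error rate is involved, so the check sets the passages side by side.

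**(a) Stop threshold: liver tumor, baseline AST and ALT not above ULN**

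| Peak AST or ALT | Table 4 through footnote b | 5.3.2 liver-tumor line |
|---|---|---|
| >3 to 5 x ULN | withhold | not met |
| >5 to 10 x ULN | permanently discontinue | not met |
| >10 x ULN | permanently discontinue | met |

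Bilirubin above 3 x ULN is a permanent stop in both texts. For subjects with liver tumor and raised baseline values, Table 4's own row also stops at >10 x ULN, as Section 5.3.2 does. The mismatch therefore comes only from footnote b and only in the middle band.

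Example: baseline normal, peak 7 x ULN. Since 7 > 5, Table 4 with footnote b gives a permanent stop. Since 7 ≤ 10, the liver line of 5.3.2 is not met. Table 4 labels this band Grade 3 or 4. If the event is graded 3, the residual line of 5.3.2 stops it only if it persists; if graded 4, a separate line of 5.3.2 stops it anyway. The difference thus concerns events graded 3.

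Such subjects can enroll. Inclusion criterion 11 caps AST and ALT at 2 x ULN (3 x with liver metastases) and sets no lower bound. They may occur in the hepatocellular cohort (14 subjects, up to 14 + 13 = 27) and in any cohort with liver metastases.

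**(b) Restart after a withheld Grade 2 pneumonitis, colitis, hepatitis or nephritis**

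| Condition | Table 4 | 5.3.4, first route | 5.3.4, second route |
|---|---|---|---|
| Grade | 0 to 1 | 1 or below, not recurrent | none |
| Steroid dose | tapered to 10 mg/day prednisone or less | none | none |
| Time limit | permanent stop if not resolved, or steroid not reducible, within 12 weeks | none | none |
| Agreement | none stated | none stated | Medical Monitor |

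Two details of Table 4: hepatitis may instead return to baseline AST or ALT after the taper, and nephritis counts its resolution limit from the last dose rather than from the start of steroids.

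Example: Grade 2 pneumonitis that after 12 weeks is still Grade 2 and stable, or still needs more than 10 mg/day prednisone. Table 4 makes the stop permanent. The second route of 5.3.4 allows restart to be considered.

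Endocrinopathies show no such conflict, because Table 4 itself accepts clinical stability there.

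**Cross-reference.** Section 5.3.3 sends temporary interruptions to 5.2.7.1, where Table 4 stands. Section 5.3.4 sends immune-related events to 5.2.5, which deals with infusion-related reactions and contains Table 3.

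**The case against.** The strongest reply is that the stop lists are cumulative. The opening of 5.3.2 asks sites to apply its criteria and to follow Table 4, and nothing there tells a site to keep dosing at or below 10 x ULN. A site that continues at 7 x ULN has read half of that sentence. This largely stands. A reader might infer that two fully compliant sites must reach opposite decisions; the text does not go that far. What remains is an explicit liver line without the baseline condition, a lead-in that mixes required with recommended, and no statement of precedence.

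Other stronger readings also go beyond the documents:

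- **Grade 3 events not named in 5.3.2.** Table 4 stops permanently for "Grade 3 or 4 diarrhea or colitis", and for Grade 3 creatinine elevation and Grade 3 neurological toxicity. One might infer that 5.3.2 downgrades these to its residual line. The lead-in brings Table 4 in, and the residual line reads naturally as covering events not governed elsewhere. Only a clarification is due.
- **Table 4 forbids what 5.3.4 allows.** Table 4 is headed as recommendations, and 5.3.4 is worded as a general rule under which restart may be considered. A specific rule normally displaces a general one, and the closing sentence of 5.3.4 suggests that immune-related events were to be handled separately. That defense is weakened because the sentence points to the wrong section.
- **Divergent handling would go unnoticed.** Immune-related events are recorded as being of special interest, with Medical Monitor involvement recommended; dosing is captured in the eCRF; the Safety Review Committee sees rolling safety data. The permission to modify refers to supportive care guidelines, and whether it reaches the withhold and discontinue column is unclear.
- **Every hepatocellular subject has liver tumor at entry.** The protocol does not say so.
- **Comparisons between cohorts are damaged.** Section 8.1 plans no formal comparisons, so this carries little weight.

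**Conclusion.** The point holds in two parts. First, the liver line of 5.3.2 and Table 4 footnote b set different AST/ALT levels for permanent discontinuation in subjects with liver tumor and normal baseline transaminases. The difference is confined to values above 5 and up to 10 x ULN; the reference to Table 4 softens it but sets no precedence. Second, the restart rule in 5.3.4 lacks Table 4's conditions for four Grade 2 immune-related events, and its cross-reference is misdirected.

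The conclusion rests on the wording alone. The protocol gives no frequency of normal baseline transaminases or of liver tumor by cohort, so the number of subjects affected cannot be stated. It takes no position on which threshold or restart rule is clinically right. Because the passages govern stopping and re-treatment, they should be reconciled even though a careful reader could find a consistent path through part of them.

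**What to change.** In the next amendment:

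1. Reconcile the liver-tumor line of 5.3.2 with Table 4 footnote b, so that one text states whether baseline values matter.
2. State whether Table 4 or the text of 5.3.2 and 5.3.4 governs immune-related events, including the Grade 3 events that Table 4 names and 5.3.2 does not. One way is to make a single text the source and have the others refer to it.
3. Correct the closing cross-reference of 5.3.4 so that immune-related events lead to 5.2.7.1 and Table 4, with 5.2.5 kept for infusion reactions.
4. Say whether the permission in 5.2.7 to modify guidance covers the withhold and discontinue column or supportive measures only.

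The sponsor's clinicians decide which threshold and which restart conditions apply. The cost is protocol wording and a memo to sites; no visits, subjects or analyses are added.

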5.3.3. Temporary Dosing Interruption

Temporary dosing interruption should occur for

- Subjects that **experience AEs for which temporary dosing interruption is recommended** as listed in [Section 5.2.7.1](#) (“Known Checkpoint Blocking Antibody-related Toxicities and Their Management”)
- Subjects who experience any other at least possibly CTL-002- or nivolumab/cemiplimab-related AE of any Grade that **in the opinion of the Investigator requires at least temporary dosing interruption** (confirmation for temporary discontinuation with the Medical Monitor is recommended for this case)

5.3.4. Recommencement of Dosing

In general, subjects may be considered for recommencement of treatment once

- A toxicity resolves to **Grade ≤ 1** (provided that the toxicity was not recurrent) or
- When a toxicity **is stable and manageable through supportive/medical therapy and in the Investigator’s opinion** and in agreement with the Sponsor Medical Monitor **it appears safe to recommence treatment**

For Part A (Phase 1), CTL-002 recommencement of treatment may be at the initial dose level or one dose level reduced, based upon the discretion of the Investigator ideally in agreement with the Sponsor Medical Monitor. For Part B (Phase 2a) of the study, recommencement of treatment should be at the same dose based upon the discretion of the Investigator ideally in agreement with the Sponsor Medical Monitor. There are no intra-subject dose escalation or reductions allowed. Dosing may only be interrupted, delayed, or discontinued.

For nivolumab, the dose is fixed at 240 mg and no dose adjustment is permitted under any circumstance apart from those provided in the label.

For cemiplimab, the dose is fixed at 350 mg and no dose adjustment is permitted under any circumstance apart from those provided in the label.

Treatment modifications for irAE and infusion-related reactions (Grade 1 to 4) should be handled according to the guidelines in [Section 5.2.5](#).

5.4. Prior and Concomitant Therapy

Any medication that is considered necessary for the subject's welfare and will not interfere with CTL-002 or nivolumab/cemiplimab (see below), may be given at the discretion of the Investigator.

5.4.1. Concomitant Therapy Guidance

Concomitant therapies should be used according to local guidance. Supportive care guidelines (Section 5.2) and prohibited medications (Section 5.4.3) must be considered.

Other anti-cancer agents, investigational agents and radiotherapy should not be given while the subject is on study, although radiation for palliation at focal sites is permitted after discussion with the Medical Monitor.

Nondrug interventions and any changes to a concomitant medication or other interventions should also be recorded in the electronic Case Report Form (eCRF). Use of any herbal or dietary supplements required to be captured with dose, start and stop dates as appropriate.

5.4.2. Recording of Concomitant Medication

Any concomitant treatment and medication information will be collected from the time that subjects sign the ICF until:

- 30 days following the last CTL-002/anti-PD-1 checkpoint inhibitor infusion
- Concomitant medications given to treat AEs deemed related to CTL-002/defined anti-PD-1 checkpoint inhibitor will be recorded up to 12 months (Part A) or 24 months (Part B) following the last CTL-002/ defined anti-PD-1 checkpoint inhibitor infusion or longer in case the AE has not resolved
- Concomitant therapies given to manage a subject's underlying disease will be recorded through the end of the study

Any medication a subject receives at the time of signing the ICF or during the study as well as any changes thereof must be recorded in the eCRF along with:

- Generic name of the drug (or trade name for combination drugs)
- Reason for use
- Dates of administration including start and end dates
- Dosage information including dose and frequency

The Medical Monitor should be contacted if there are any questions regarding concomitant medication or prior therapy.

In addition, any prior or concomitant diseases and signs and symptoms (a condition that is either active at enrolment or adversely impacts the subject's condition at enrolment), if applicable at baseline will be recorded. The Sponsor will code according to the standard dictionaries (e.g., WHO Drug and Medical Dictionary for Regulatory Activities [MedDRA]); for details refer to the Safety Management Plan.

5.4.3. Prohibited Medications

The following are prohibited during the study:

- Chemotherapy, surgery or radiation therapy for cancer are not allowed during active participation with the exception of palliative intent. Likewise, use of any unapproved (i.e., no marketing authorization has been granted) IMP, other than CTL-002/the defined anti-PD-1 checkpoint inhibitor, or device is not allowed until a subject has completed the End of Core Study/Safety Follow-up Visit and enters the long-term Follow-up Period part of the study
- Corticosteroids and other immunosuppressive compounds are prohibited during active participation, except for:
 - a. Inhaled or topical steroids for short term use.
 - b. Prednisone or equivalent used to treat any condition other than immune-mediated AEs at a dose of ≤ 0.125 mg/kg/day of prednisone (maximum allowed 10 mg/day) for more than 7 consecutive days or at a dose of >0.125 mg/kg/day prednisone for less than 7 consecutive days.
 - c. Corticosteroids used to treat immune-mediated AEs.
 - d. Immunomodulating agents.
 - e. Anti-PD-1 checkpoint inhibitor determined as combination treatment product in this protocol.

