2.3. Optional Stereotactic Radiotherapy

All subjects in the phase 2 part that achieve/maintain stable disease by week 24 but do not show tumor shrinkage beyond -10% as per RECIST criteria can undergo if desired by the treating physician and agreed by the patient stereotactic radiotherapy of one or more tumor lesions to increase neoantigen exposure and potential for response improvement (as was seen in two phase 1 patients). This should always be pre-discussed with the medical representative of the sponsor and the radiotherapy area should not include all lesions that are used for RECIST response assessment to allow for abscopal antitumor effect assessment.

Radiotherapy should be performed according to local hospital's regulations.

Note: In case of initiation of stereotactic radiotherapy in addition to study treatment, an optional tumor biopsy should be performed no earlier than 4 weeks after initiation of radiotherapy, if seen as safe and medically feasible by the treating physician.

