3.3. Discontinuation of Study Treatment and Subject Withdrawal Criteria

Subjects are at any time free to withdraw from the study, without prejudice to further treatment (withdrawal of consent). Such subjects will always be asked about the reason(s) and the presence of any AEs. If possible, they will be seen by an Investigator and undergo the End of Treatment Visit (see [Section 6.1.9](#)) and assessments and procedures scheduled for the follow-up (see [Section 6.1.11](#)). Adverse Events should be followed up (see [Section 7.2.1](#)). More detailed guidance on Dose Modification and Discontinuation criteria is given in [Section 5.3](#).

Subjects must be discontinued from the study in the following situations:

1. Occurrence of any AEs that are deemed to be clinically significant in the opinion of the Investigator and/or the SRC and warrant that a subject must discontinue treatment and be withdrawn from the study.
2. DLT in Part A (Phase 1; dose escalation).
3. Severe non-compliance to this protocol as judged by the Investigator and/or the SRC.
4. Confirmed disease progression.
5. Subjects incorrectly initiated on CTL-002 or the defined checkpoint inhibitor.
6. Use of prohibited concomitant drug, as defined in [Section 5.4.3](#).
7. Pregnancy.
8. Withdrawal of consent.
9. Participation in any other clinical trial.

3.4. Procedures for Handling Subjects Incorrectly Initiated on CTL-002 and/or the Defined Checkpoint Inhibitor

Subjects who fail to meet the inclusion/exclusion criteria should not, under any circumstances, be enrolled to receive study medication. There can be no exceptions to this rule.

Where subjects who do not meet the inclusion criteria and have been enrolled or started treatment with CTL-002 (or the defined checkpoint-inhibitor) in error, the Investigator shall inform the Medical Monitor and the SRC immediately. The Investigator will discuss with the SRC and the subject the best way forward and whether study treatment should be aborted or continued. The decision making has the intent to provide the subject with the best possible solution for his/her situation. The Investigator and Medical Monitor are to ensure that all such decision making is appropriately documented.

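### Section 2.3 offers stereotactic radiotherapy to improve response, but Sections 5.4.1 and 5.4.3 allow radiation on study only for palliation, and whether Section 3.3 item 6 applies is unclear

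*Protocol*

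**What the plan says.** **The offer.** Protocol Section 2.3 allows Phase 2 subjects who have stable disease by week 24, without shrinkage beyond 10%, to receive "stereotactic radiotherapy of one or more tumor lesions to increase neoantigen exposure and potential for response improvement". The treating physician must want it, the patient must agree, and it is to be discussed beforehand with the sponsor's medical representative. The section's note on biopsies opens with "In case of initiation of stereotactic radiotherapy in addition to study treatment", so the radiotherapy is added to ongoing CTL-002 and checkpoint inhibitor. The same option appears in the Synopsis (twice) and in Sections 1.8.4, 2.1 and 2.2.2.

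**The endpoints that depend on it.** Section 1.9.3 has two exploratory Part B objectives in subjects with stable disease who receive this radiotherapy. Section 1.10.3 defines the post-radiotherapy endpoints ORR-2, TTR-2 and DOR-2.

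**The restrictions.** Section 5.4.1: "radiotherapy should not be given while the subject is on study, although radiation for palliation at focal sites is permitted", the last part subject to discussion with the Medical Monitor. Section 5.4.3 names chemotherapy, surgery and radiation together and ends: "radiation therapy for cancer are not allowed during active participation with the exception of palliative intent".

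**The discontinuation rule.** Section 3.3 opens its list with "Subjects must be discontinued from the study in the following situations". Item 6 reads "Use of prohibited concomitant drug, as defined in" Section 5.4.3.

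**The concern.** The same intervention is offered in one part of the protocol and restricted in another. The stated aim in Section 2.3 is antitumor response, whereas the only exception in Sections 5.4.1 and 5.4.3 is palliation. Neither restriction refers to Section 2.3.

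A site that works from Section 5.4 may withhold the radiotherapy. A site that works from Section 2.3 may give it and have it recorded as a deviation. Some may go further and discontinue the subject under Section 3.3. The Synopsis plans up to 22 sites for Part B, so different sites may well resolve the conflict differently.

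What is at stake statistically is the composition of the group behind ORR-2, TTR-2 and DOR-2. It could vary with each site's reading of the protocol, and a reader of the results could not tell that apart from clinical selection.

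**Working it through.** No sample size, power or event count is involved, so there is nothing to compute. The check is a comparison of the sections.

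1. **Is the subject still covered by the restrictions when the radiotherapy is given?** Yes. Section 5.4.1 applies while the subject is on study, and Section 5.4.3 during active participation. Section 2.3 adds the radiotherapy to continuing study treatment, so both apply.

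2. **Does the palliative exception cover it?** Not on the stated purpose. Section 2.3 names neoantigen exposure and response improvement, and asks that some RECIST lesions stay outside the radiation field so that an abscopal effect can be assessed. Section 1.3 presents the radiotherapy as a way to optimize immunotherapy. The protocol does not define palliative intent. If the term meant no more than non-curative, the exception would cover everyone, because inclusion criterion 3 in Section 3.1 requires every subject to be in a non-curable state. The same exception governs chemotherapy and surgery, so that reading would leave the first prohibition in Section 5.4.3 with nothing to prohibit.

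3. **Is there an exemption elsewhere?** None was found. Sections 3.3, 5.4.1 and 5.4.3 do not mention Section 2.3. Section 5.4.3 does exempt other protocol treatment where that was wanted: CTL-002 and the checkpoint inhibitor are excepted from the ban on unapproved products, and the checkpoint inhibitor appears again among the exceptions to the immunosuppressant ban. Section 5.1 recognises radiotherapy as a possible source of added toxicity, so Section 5 knows of the option while Section 5.4 still excludes it.

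4. **Does Section 3.3 item 6 apply?** The text does not settle this. Item 6 says "Use of prohibited concomitant drug", and radiotherapy is not a drug. But it takes its definition from Section 5.4.3, whose heading refers to medications and whose first entry includes radiation therapy. Either reading can be defended.

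5. **What follows for the endpoints?** Under Section 5.4 taken alone, no subject may receive the radiotherapy for the purpose in Section 2.3. Under Section 2.3 taken alone, subjects receive it and contribute data. If a subject received it and was then discontinued, imaging would move from the fixed schedule (every 8 weeks, or 6 to 9 weeks in the cutaneous squamous-cell cohort) to local practice during follow-up (Sections 6.1.11 and 6.2.5.1). The data would be less regular, but not necessarily absent.

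**The case against.** The best reply is that the protocol read as a whole plainly intends this radiotherapy to be given. It has a rationale (Section 1.3), a risk section (1.8.4), a place in the benefit-risk conclusion (1.8.5), objectives, endpoints, a toxicity item (5.1) and biopsy instructions (6.2.1, Tables 6 and 7). On that view Section 5.4 is general text about radiotherapy outside the provision. Section 5.4.1 says only that radiotherapy should not be given, and the required discussion with the sponsor makes unnoticed differences between sites less likely. The radiotherapy is elective in any case, so the group would be selected even with perfect wording.

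Much of this stands. The intention is clear, the elective selection would remain after any repair, and sponsor contact offers some protection. What it does not do is remove the conflict. The protocol has no rule that a specific provision overrides a general one, and a monitor checking Section 5.4.3 finds an explicit prohibition without this exception.

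A reader might go further and infer that Section 3.3 makes discontinuation mandatory for everyone who uses the option, so that the post-radiotherapy endpoints cannot be observed and no such subject can contribute. The documents do not support that. Item 6 speaks of a drug, and Section 5.4.1 mentions nondrug interventions separately when it sets out what to record. Sites that follow Section 2.3 would generate the data, and tumor imaging can continue in follow-up.

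**Conclusion.** The contradiction between Section 2.3 and Sections 5.4.1 and 5.4.3 is real and is not resolved anywhere in the protocol. The reach of Section 3.3 item 6 is an ambiguity that makes it worse; mandatory discontinuation is one possible reading, not an established consequence.

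The effect is limited to two exploratory objectives and three exploratory endpoints. Section 8.1 describes the study as explorative, with no formal comparisons. The protocol does not say how many subjects are expected to use the option, so the effect cannot be put as a number of subjects.

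The conclusion rests on two assumptions: that palliative intent carries a narrower meaning than non-curative, for the reason given in the check, and that sites may act on Section 5.4 as written. It is worth correcting because the conflict concerns who may receive an intervention on which stated endpoints depend.

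**What to change.** Reconcile Section 2.3 with Sections 5.4.1 and 5.4.3, so that each says the same thing about radiotherapy given under Section 2.3. State in Section 3.3 item 6 whether such radiotherapy falls under it. Which rule stands is for the sponsor's clinical team, and nothing here argues for either.

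If the option in Section 2.3 is kept, the cost is one clause in each of three sections: 3.3 item 6, 5.4.1 and 5.4.3. If the restriction is kept, the edits are wider: Section 2.3 and the places that repeat it, the two objectives, the three endpoints and the related biopsy instructions. In either case the sample size is unaffected.
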